# 7.4.8 Reproductive and Developmental Risks

Risks posed by MDMA to pregnant women are not known. One of two studies of Ecstasy users suggests that use of Ecstasy and other drugs during pregnancy may be associated with some abnormalities at birth while the other failed to find this association, [165, 166]. A survey reported that in women interviewed on their drug use during pregnancy, there was a link between self-reported extent of prenatal MDMA exposure and delays in infant development at 12 months [167]. Pregnant and lactating women will be excluded from participation in the proposed protocol, and women who are able to become pregnant must have a negative pregnancy screen before undergoing each experimental session and must agree to use birth control during the period of the protocol. If any participant becomes pregnant after the occurrence of at an experimental session, the sponsor and Clinical investigator will follow the pregnancy to outcome.

#### 7.5 Medical Emergencies

The preparatory session, MDMA session and integrative session, will be conducted in the psychiatric offices of the investigators. The offices are located 2.6 miles from the nearest emergency room. The office will be equipped with a "crash cart" containing the emergency drugs and equipment necessary to respond to any complications. Intravenous fluids, antiarrhythmic drugs, antihypertensive drugs (such as nitroprusside and labetolol), injectable epinephrine and other pressor agents, and other standard emergency drugs and equipment will be available on-site as a means of treating any potential allergic reactions or other medical emergencies. In addition to drugs, the crash cart will contain a defibrillator (with rhythm monitoring capability), an oxygen tank, a suction device, a pulse oxometer, an IVAC pump and intubation equipment (including laryngoscope, and endotracheal tubes). As is now common practice in emergency departments, an automatic blood pressure cuff will be used in place of intraarterial blood pressure monitoring equipment. For a recently completed Phase 2 trial, the researchers have established (in communication with the FDA) contingency plans for responding to those AEs that appear most likely, based on a comprehensive review of case reports of toxicity in illicit MDMA users reported by Baggott and colleagues in 2001 and in the current Investigator's Brochure. The same contingency plans and equipment will be used in this protocol, with the exception of the fact that there will not be an additional nurse on site

for this study. In the unlikely event of cardiac arrest, the researchers will follow the American Heart Association guidelines for 2-person BLS for Healthcare Providers (including defibrillation with an automated external defibrillator (AED) until the arrival of Emergency Medical Services (EMS), at which time Advanced Cardiac Life Support (ACLS) procedures will be instituted. With these personnel and equipment, the researchers, in conjunction with EMS if necessary would be able to begin treatment in the office and then transport the participant by ambulance if hospital admission were required.

#### 8.0 Adverse Events

An Adverse Event (AE) is defined as any untoward or unfavorable medical occurrence in a clinical research study participant, including any abnormal sign (e.g. abnormal physical exam or laboratory finding), symptom, or disease, temporally associated with the participants' involvement in the research, whether or not considered related to participation in the research. This definition includes concurrent illnesses or injuries and exacerbation of pre-existing conditions.

An unexpected adverse event is one that is not listed in the current Investigator's Brochure or an event that is by nature more specific or more severe than a listed event. All AEs will be monitored by the investigators until resolution or, if the AE becomes chronic, a cause identified. If an AE is unresolved at the conclusion of the protocol, a clinical assessment will be made by the investigator and/or Medical Monitor as to whether continued follow-up of the AE is warranted.

The severity of events reported on the "Adverse Events" CRF will be determined by the investigator as:

- · Mild: No limitation in normal daily activity
- · Moderate: Some limitation in normal daily activity
- · Severe: Unable to perform normal daily activity

The relationship of the study treatment to an AE will be determined by the investigator based on the following definitions:

#### 1. Not Related

The AE is not related if exposure to the investigational product has not occurred, or the occurrence of the AE is not reasonably related in time, or the AE is considered unlikely to be related to use of the investigational product, i.e. there are no facts (evidence) or arguments to suggest a causal relationship, or the AE is more likely related to the subject's pre-existing condition.

#### 2. Possibly Related

The administration of the investigational product and AE are considered reasonably related in time and the AE could be explained by causes other than exposure to the

investigational product.

# 3. Probably Related

Exposure to the investigational product and AE are reasonably related in time and the investigational product is more likely than other causes to be responsible for the AE, or is the most likely cause of the AE.

The relationship of the study treatment to an AE will be determined by the investigator.

#### **8.1 Common Expected Reactions**

Commonly expected reactions that are spontaneously reported are collected on a separate CRF page and will be categorized as mild, moderate or severe. Spontaneously reported reactions may include reduced appetite, dizziness, tight jaw or bruxism (tooth-grinding), difficulty concentrating, impaired gait or balance, dry mouth, and thirst. Other slightly less common reactions include drowsiness, impaired judgment, headache, restlessness, nausea, parasthesias (odd somatic feelings, such as tingling, feeling hot or cold), changes in thought, perspiration, drowsiness, nystagmus (eye-wiggling) and sensitivity to cold. These effects are transient and wane as drug effects wane. Sub-acute effects that may either continue for the next 24 hours or appear later include insomnia, fatigue, weakness, heavy legs, dry mouth, low mood or irritability. Sub-acute effects are reported less often than acute effects. Other spontaneously reported reactions include increased private worries (rumination) and needing more sleep. Sub-acute effects are reported less often than acute effects. Other common reactions in preliminary data from the initial study of MDMA-assisted psychotherapy in people with PTSD include muscle tension in approximately 20% and gastrointestinal discomfort or diarrhea in approximately 3.3% participants receiving MDMA. Spontaneously reported reactions will be collected during the experimental session and during the seven days of telephone contact beginning the day after each experimental session.

#### **8.2 Serious Adverse Events**

An SAE is defined as any untoward medical occurrence that at any dose:

- Results in death
- Is life-threatening (i.e., the subject was, in the opinion of the investigator, at immediate risk of death from the event as it occurred); it does not refer to an event which hypothetically might have caused death if it were more severe
- Requires or prolongs inpatient hospitalization
- Results in persistent or significant disability/incapacity (i.e., the event causes a substantial disruption of a person's ability to conduct normal life functions)
- Results in a congenital anomaly/birth defect
- Requires intervention to prevent permanent impairment or damage
- Is an important and significant medical event that may not be immediately lifethreatening or resulting in death or hospitalization, but based upon appropriate medical judgment, may jeopardize the patient/subject or may require intervention to prevent one of the other outcomes listed above

AEs which do not fall into these categories are defined as non-serious. It should be noted that a severe adverse event need not be serious in nature and that a SAE need not, by definition, be severe.

In addition, a pre-existing event or condition that results in hospitalization should be recorded on the medical history. The hospitalization would not result in the event or condition being reported as a study-related SAE unless, in the view of the investigator, hospitalization was prolonged as a result of participation in the clinical trial or was necessary due to a worsening of the pre-existing condition. This is because the onset of the event (the reason for the procedure) occurred before the subject was entered in the trial. Hospitalization for cosmetics, non-emergency prophylaxis or abortion does not result in an SAE report unless, in the view of the investigator, hospitalization for these procedures was prolonged as a result of participation in the clinical trial.

#### **8.3 Adverse Event Collection**

All SAEs will be collected for the duration of the protocol. All SAEs which occur during the course of the trial, whether considered to be associated with the study drug or not, have to be reported within 24 hours or at the latest on the following working day by telephone or fax to either of the following:

#### **Study Monitor:**

[name].

[contact] ext. 104

[contact] Email: [contact]

Adverse events (AEs) that will be collected for the duration of the protocol are:

- All SAEs will be collected from enrollment through termination.
- All AEs and common expected reactions will be collected on the day of MDMA administration and for seven days after each experimental session.
- Events requiring medical attention will be collected from the first experimental session through the subject's final assessment at the end of Stage 1 or Stage 2 (as appropriate).

- Events related to planned treatments or physician visits for baseline conditions collected in the Medical History will not be collected unless there is an exacerbation of the condition.
- Any AE leading to withdrawal from the protocol will be collected throughout the study.
- All AEs related to changes in psychiatric status will be collected throughout the study.

A Memory aid card will be provided to the subject on the last visit prior to the 12 month follow up to record information on medications taken to treat SAEs, AEs leading to withdrawal and psychiatric AEs during the period between the end of Stage 1 or end of Stage 2 and the 12 month follow-up evaluation. The memory aid card will not be collected, but information from the card will be used to aid the subjects in providing information to the investigator. This information may be collected by phone.

# 9.0 Collection of Concomitant Medications and Tapering Instructions

All medications, over the counter (OTC) and prescription will be collected from screening through 7 days after the final experimental session. From 7 days after the final experimental session through study termination only medications taken to treat SAEs and psychiatric AEs will be collected.

Concomitant medications will be recorded during screening. Any psychoactive drugs will be tapered in an appropriate fashion to avoid withdrawal effects. They will be discontinued long enough before the experimental session to avoid the possibility of drug interactions (the interval will be at least 5 times the half-life of the particular drug or its active metabolites, plus one week for stabilization). If necessary, the investigators will make plans for tapering off and discontinuing any contraindicated medication upon enrollment, in consultation with the prescribing physician.

The investigators will request information about any changes in medication. Medications taken during the course of the protocol, including medications taken to treat AEs, will be recorded on a concomitant medications CRF. Participants must be willing to refrain from taking any psychiatric medications until after the end of Stage 1 or Stage 2, with the exception of gabapentin when prescribed for pain control or stimulants for ADHD taken at baseline provided that they are discontinued 5 half lives before each MDMA session and are not restarted until 10 days after each MDMA administration. The investigators may prescribe a designated rescue medication in the event of symptoms that require it during or after the experimental session (e.g. insomnia or severe anxiety that does not respond to other management outlined in the treatment manual).

Subjects must be willing to refrain from taking any psychiatric medications during Stage 1 and Stage 2, with the exception of gabapentin when prescribed for pain control. If the subject is on stimulants for ADHD at baseline, they can continue to use them at the same dose and frequency as long as they discontinue five half-lives before each experimental session and do not restart for 10 days after each experimental session.

**Medication Tapering Table** 

Generic Name	Brand Name	Half-life (hours)	Days for Washout
		including active metabolites	
alprazolam	Xanax	11	3
aripiprazole	Abilify	75	16
atomoxetine	Strattera	5-24	5
bupropion	Wellbutrin	21	5
citalopram	Celexa	35	8
clonazepam	Klonopin	30-40	8
diazepam	Valium	20-70	15
duloxetine	Cymbalta	12	3
escitalopram	Lexapro	32	7
fluoxetine	Prozac	7-9 (days)	45
imiprimine	Tofranil	6-18	4
lamotrigine	Lamictal	25	6
lorazepam	Ativan	12	3
mirtazapine	Remeron	20-40	8
olanzapine	Zyprexa	21-54	11
paroxetine	Paxil	21	5
prazosin	Minipress	2-3	1
quetiapine	Seroquel	6	2
risperidone	Risperdal	3-20	4
sertraline	Zoloft	26	6
temazepam	Restoril	8-12	3
trazodone	Desyrel	9	2
venlafaxine	Effexor	12	3
ziprazidone	Geodon	7	2
zolpidem	Ambien	2.5	<1

The CI may prescribe a designated rescue medication in the event of symptoms that require it during or after the experimental session (e.g. insomnia or severe anxiety that does not respond to other management outlined in the treatment manual). Rescue medications may be a benzodiazepine, zolpidem or other anxiolytic or sedative according to the physician's clinical judgment. SSRIs, SNRIs, and MAOIs should not be used as rescue medications.

Participants must agree that, for one week preceding the MDMA session:

- a. Subjects will refrain from taking any herbal supplement (except with prior approval of the research team).
- b. Subjects will not take any nonprescription medications (with the exception of non-steroidal anti-inflammatory drugs or acetaminophen unless with prior approval of the research team).

c. With the permission of their physician subjects will not take any prescription medications (with the exception of birth control pills, thyroid hormones or other medications approved by the research team).

# 10.0 Clinical Laboratory Assessments

The Clinical Investigator will examine laboratory assessments gathered in screening for assessing participant eligibility. The investigator will use a list of normal ranges to conclude whether participants are eligible for the protocol, and will indicate justification for admitting participants with abnormal values.

The following laboratory assessments will be performed as a part of screening:

Serum electrolytes and the **metabolic profile**, which includes:

```
ALT/SGPT;
albumin:globulin (A:G) ratio;
albumin, serum;
alkaline phosphatase, serum;
AST/SGOT:
bilirubin, total;
BUN;
BUN: creatinine ratio;
calcium, serum;
carbon dioxide;
chloride, serum;
creatinine, serum;
globulin, total;
glucose, serum;
potassium, serum;
protein, total, serum;
sodium, serum;
```

## CBC, which includes:

Hematocrit;
hemoglobin;
MCV;
MCH;
MCHC;
RDW;
percentage and absolute differential counts;
RBC;
red cell count;
WBC;

#### Urinalysis, which includes:

Color;

appearance; specific gravity; pH; protein; glucose; ketones; occult blood; leukocyte esterase; nitrite; bilirubin; urobilinogen;

## Thyroid function, which includes:

TSH high sensitivity;

Free T4:

Free T3.

In addition, HIV and, if indicated, Hepatitis C serology will be performed.

A urine-dip pregnancy test for females of childbearing potential and a urinary drug screen will be performed as well.

The laboratory assessments other than the urine drug screen and pregnancy test will be performed at:

Laboratory Corporation of America [name]

The urine drug screen and pregnancy test will be performed at the study site.

#### 11.0 Study Monitoring, Auditing and Documentation

Investigators and/or their study staff will be trained prior to the start of the protocol. The clinical study site will be monitored by site visits and telephone calls to the investigator by representatives of the sponsor. The site will be monitored as appropriate for the rate of enrollment in order to comply with GCP guidelines and to ensure validity of the study data. From the start of the study, videos from selected sessions will be reviewed for adherence to the Treatment Manual and therapeutic alliance. Adherence will be checked by monitoring and by review of selected video data. During each monitoring visit, source data verification will be performed by a Clinical Research Associate (CRA) to ensure compliance, including accurate and complete recording of data on CRFs, source documents, and drug accountability records. A CRF collation supplied by the sponsor will be completed for each participant enrolled. Monitoring and auditing procedures of the sponsor will be followed, in order to comply with Good Clinical Practice (GCP) guidelines and to ensure validity of the study data.

The sponsor will review the study documentation used for planning, conduct and

monitoring of the study in order to ensure compliance with GCP and local regulations. This documentation includes as a minimum: the Investigator's Brochure, the Study Protocol, the Case Report Forms and the Subject Information and Consent Form.

During or after the clinical protocol, the regulatory authorities, the IRB, and/or representatives of the sponsor may request access to all source documents, CRFs and other protocol documentation for on-site audit or inspection.

### 12.0 Data Analysis

The Sponsor will judge the clinical and statistical significance of the study and estimate effect size and statistical power based on a comparison of observer-blind data collected at baseline and the primary endpoint using the primary outcome measure, which is the CAPS.

The sample selection is expected to produce acceptably homogeneous groups due to their diagnosis of with PTSD with CAPS scores of at least 50 who have not responded to treatment. There is no expectation that conditions will differ significantly in composition by gender, race or ethnicity, duration of PTSD diagnosis or presence versus absence of other permitted psychiatric disorders, as depression.

The sponsor will examine individual CAPS, BDI-II, PTGI, PSQI, DES-II and GAF scores at baseline and the primary endpoint, in low dose, medium dose and full dose conditions. Descriptive statistics will be calculated for all measurements overall and by condition. Distributional characteristics will be examined for outliers and extreme values and, if either is evident. If outliers are found in primary or secondary outcome measures, the sponsor will perform analyses with and without the outlying data. Effect sizes for all outcome measures for primary endpoint, Stage 1, secondary endpoint, end of Stage 2, and 12-month follow-up will be estimated using Cohen's techniques.

All analyses of data from the primary endpoint will contain blinded data. Analysis of variance will be used to compare Global CAPS scores by dose condition at the primary endpoint.

Analysis of variance, or nonparametric analysis if assumptions are not met, will be used to compare the dose conditions for change in BDI-II, PTGI, PSQI, GAF, DES-II and NEO PI scores separately. If scores cannot be examined sufficiently in this model, then analyses will compare available data through the use of difference scores.

The sponsor will examine open-label data collected two months after the third Stage 1 experimental session. The sponsor will perform a within-subject analysis of full dose participants.

Subjects who discontinue treatment prior to the primary endpoint will be asked to complete an outcome assessment prior to continuing to the long-term follow-up. The data from these subjects will be tested for equivalence to data from subjects completing the study per protocol. If found to be equivalent, data from these subjects will be presented as

an exploratory intent to treat analysis to examine results without bias towards subjects more likely to complete the study per protocol.

Descriptive statistics will be computed for vital signs and subjective distress during each experimental or open-label session. The sponsor will informally or formally compare peak blood pressure, heart rate and body temperature for participants after sessions after low, medium or full dose MDMA. Frequency tables will be produced on prevalence of spontaneously reported reactions and AEs.

The sponsor will collect Changes in Tinnitus and/or Pain visual analog scale scores from any subject reporting tinnitus or chronic pain during each point of administration, including baseline, experimental and integrative sessions, the primary endpoint, and two-month follow-up. The sponsor will plot and examine all Changes in Tinnitus and/or Pain visual analog scale scores across all three groups and within the dose groups for trends. Formal analysis of Changes in Tinnitus and/or Pain visual analog scale scores will only occur if three or more subjects complete Changes in Tinnitus and/or Pain visual analog scale at baseline and primary endpoint. Likewise, formal between-groups analyses will not be performed if all primary endpoint scores are from subjects assigned to the same condition. The sponsor will perform an independent t-test on the difference between baseline and primary endpoint Changes in Tinnitus and/or Pain visual analog scale scores in the full dose and comparator dose conditions, with p. set at 0.05. If the only scores available are for subjects in a single condition, then a paired t-test will be performed comparing baseline and primary endpoint Changes in Tinnitus and/or Pain visual analog scale scores, with p. set at 0.05.

Descriptive statistics will be computed for SOCQ scores completed after each MDMA-assisted psychotherapy session, and SOCQ scores will be compared across each of the three MDMA dose conditions and after full dose given during Stage 2. The data will be explored for effects of condition on responses to the SOCQ.

Descriptive statistics will be calculated for subject's perceptions of experimental sessions. Mean, standard deviation and range of individual responses will be examined. Perceptions of experimental sessions will be examined during Stage 1 and Stage 2, before and after participant have undergone a third experimental session and will be compared within subjects.

The sponsor will collect ratings of adherence to the treatment manual from specifically selected types of sessions. Descriptive statistics will be computed for each adherence scale within a given session. The sponsor will explore the factors and structure of the measures of adherence to assist in further development of adherence and competence measures. If sufficient data is available, the sponsor will correlate the mean adherence ratings for adherence scale and session type with Global CAPS scores to investigate the effects of adherence to the treatment manual on reduction in PTSD symptoms. If it is found that there are specific factors within the adherence scales, then the factor will be correlated with Global CAPS score.

Qualitative interviews conducted by a researcher who is part of the study team during the 12-month follow-up visit will be transcribed to text. A computer-assisted qualitative data analysis software package will be utilized to assist in thematic content analysis of the interview transcripts. A member of the research team will code the interviews for content, to identify emerging themes and organize data into thematic constructs utilizing a grounded theory approach. Descriptive statistics will be calculated for emerging themes.

There may be an interim analysis of the data that will not affect study conduct for safety and efficacy before all participants have completed the 12-month follow-up.

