### 3.0 Protocol Objectives

The overall objective of this study is to explore the safety and estimate the effect size of efficacy for MDMA-assisted psychotherapy in veterans, firefighters and police officers with PTSD, a group with a different index trauma from most subjects in prior

investigations of this experimental treatment.

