## **5.0 Randomization and Blinding**

This is a randomized, triple-blind, dose response study with an open-label cross-over segment. For Stage 1, a randomization list will be prepared at the beginning of the study. If needed, subsequent randomization lists will be created to replace subjects who withdraw from the study to ensure that replacement subjects are not added to the end of the initial list. Each subject will be assigned to one of the three dose conditions; 30 mg (low dose), 75 mg (medium dose) or 125 mg (full dose). Twelve evaluable subjects will be assigned to the full dose condition, six evaluable subjects to the 75 mg condition and six evaluable subjects to the 30 mg low dose condition. The study will employ a blinded randomization procedure that will maintain the 2:1:1 ratio while maintaining the blind and ensuring that each subsequent condition assignment is not predicated on the previous assignment.

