## **6.0 Sample Size and Power Considerations**

This study is a pilot investigation intended to gather preliminary data on the safety and efficacy of MDMA in 24 evaluable veterans, firefighters, or police officers with chronic, treatment-resistant PTSD. Because of their exploratory nature, pilot studies are often not powered for detecting the desired effect. Because it is a pilot study in a small sample, results will be used to collect effect size estimates for statistical power calculations for adequately powered subsequent studies.

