## **8.9 Efficacy Analyses**

For all primary, secondary and exploratory endpoints descriptive statistics (n, mean, standard deviation, median, range, or counts and percentages where appropriate) will be provided by treatment group.

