## **8.9.2 Secondary Efficacy Analyses**

### **8.9.2.1 Secondary Efficacy Analyses at Primary Endpoint**

The secondary efficacy analyses will be made with ANOVA comparing change from baseline (visit 1) to the primary outcome timepoint (visit 13) of all the secondary measures. If the parametric assumptions for the ANOVA analyses are not met, the analogous nonparametric methods will be used (Kruskall-Wallis, Wilcoxon Rank-Sum).

Clinician Administered PTSD Scale-4 (CAPS-4) global scores will also be analyzed for effect size with the Cohen's *d* analysis.

Global Assessment of Functioning (GAF) total score will be analyzed in the same manner as the CAPS-4 global scale primary analysis.

Beck Depression Inventory-II (BDI-II) total score will be analyzed in the same manner as the CAPS-4 global scale primary analysis.

Post Traumatic Growth Inventory (PTGI) total will be analyzed in the same manner as the CAPS-4 global scale primary analysis.

Dissociative Experiences Scale-II (DES-II) total will be analyzed in the same manner as the CAPS-4 global scale primary analysis.

Pittsburgh Sleep Quality Index (PSQI) global scores will be analyzed in the same manner as the CAPS-4 global scale primary analysis.

NEO Personality Inventory (NEO PI) five factor scores will be analyzed in the same manner as the CAPS-4 global scale primary analysis.

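### Effect-size estimation is part of the overall objective, but the plan gives only an undefined, uncorrected Cohen's d with no confidence interval in arms of 12, 6 and 6

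*Protocol*

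**What the plan says.** - **Aim.** The overall objective in Protocol 3.0 is to "explore the safety and estimate the effect size of efficacy" of the treatment. SAP 6.0 gives the use: "results will be used to collect effect size estimates for statistical power calculations for adequately powered subsequent studies".
- **Method in the Protocol.** Section 12.0 says the sponsor will "estimate effect size and statistical power based on a comparison of observer-blind data collected at baseline and the primary endpoint". It then promises effect sizes for all outcome measures at five time points, the list ending "12-month follow-up will be estimated using Cohen's techniques".
- **Method in the SAP.** Section 8.9.2.1, under secondary analyses, says CAPS-4 "global scores will also be analyzed for effect size" by Cohen's *d*. The other secondary measures are to be handled like the CAPS-4 primary analysis, which is an ANOVA and contains no *d*.
- **Summaries.** SAP 8.9 provides, by treatment group, "descriptive statistics (n, mean, standard deviation, median, range, or counts and percentages where appropriate". SAP 8.0 fixes how p-values are displayed. Neither document mentions a confidence interval or a small-sample correction.
- **Size.** SAP 5.0: "Twelve evaluable subjects will be assigned to the full dose condition", with six each in the 75 mg and 30 mg conditions.

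**The concern.** If the effect size is to be an input to later trials, its precision matters as much as its value. With 18 or 12 subjects in a pairwise comparison, a point estimate of *d* is compatible with a very wide range of true effects, and the plan schedules nothing that would show this. *d* is also undefined. The documents do not say whether it is between or within arms, which dose contrasts it covers, or whether it is scaled by the baseline, endpoint or change-score SD. Different choices can give different values from the same data.

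Two lesser matters go with this. Uncorrected *d* is biased upward in small samples. And estimating statistical power from the observed comparison, taken literally, yields a number that is fixed by the p-value.

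At stake are the reporting of the effect and the sizing of the next trial. The validity of the primary test is not.

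**Working it through.** **Inputs.** Arms of 12, 6 and 6 (SAP 5.0); two-sided tests at 0.05 (SAP 8.0 and 8.9.1). The documents state no assumed effect, SD or target power, so there is no figure of the plan's own to reproduce. The values of *d* and the power targets below are assumptions. So is the form of *d*: between-arm, two-group pooled SD, normal data with common variance.

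**Step 1: link *d* to *t*.** t = d × √(n₁n₂/(n₁+n₂)).
- 12 v 6 (full v low, or full v medium): √(72/18) = 2.000, df = 16.
- 6 v 6 (medium v low): √(36/12) = 1.732, df = 10.

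**Step 2: 95% CI for *d*.** Find the two noncentrality values that place the observed *t* at the 97.5th and 2.5th percentiles of the noncentral *t*, then divide by the factor in step 1.

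| Assumed observed *d* | 12 v 6 | 6 v 6 |
|---|---|---|
| 0.5 | -0.50 to 1.49 | -0.66 to 1.64 |
| 0.8 | -0.23 to 1.81 | -0.40 to 1.97 |
| 1.0 | -0.05 to 2.02 | -0.23 to 2.19 |
| 1.5 | 0.37 to 2.59 | 0.17 to 2.78 |

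The width is 1.99 to 2.21 units at 12 v 6 and 2.30 to 2.61 at 6 v 6. The smallest *d* that reaches p = 0.05 is 2.120/2.000 = 1.06 and 2.228/1.732 = 1.29 respectively.

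**Step 3: small-sample bias.** J = 1 - 3/(4df - 1), and g = J × d.
- df 16: J = 1 - 3/63 = 0.952, so *d* overstates by 1/0.952 - 1 = 5.0%.
- df 10: J = 1 - 3/39 = 0.923, an overstatement of about 8%.
- Three-arm ANOVA error term, df = 24 - 3 = 21: J = 1 - 3/83 = 0.964, an overstatement of 3.8% for every contrast.

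**Step 4: effect on a later two-arm trial** (two-sided 0.05, 90% power, *t*-test).
- d = 1.0 gives 23 per arm.
- Corrected to 0.952 or 0.923, it gives 25 or 26 per arm.
- d = 0.5, well inside both intervals for an observed 1.0, gives 86 per arm.
- At the lower limits, which are below zero, no finite sample size exists.

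The correction moves the answer by two or three subjects per arm. Sampling uncertainty moves it by a factor of nearly four (86/23 = 3.7) before the limit of the interval is reached.

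**Step 5: observed power.** For a given design, power evaluated at the observed *d* depends only on the observed *t*, and hence only on p. A result exactly at p = 0.05 gives 0.51 (12 v 6) or 0.52 (6 v 6). With a true *d* of 0.8 at 12 v 6, true power is 0.325. Over 20,000 simulated trials, observed power ran from 0.06 to 0.92 (5th to 95th percentile).

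**The case against.** **The power wording may be harmless.** A reader might infer from Protocol 12.0 that the trial will report its own observed power. The documents do not settle that. The SAP contains no such step anywhere in section 8, and SAP 6.0 describes power calculations for subsequent studies, which is legitimate. What stands is that the Protocol sentence does not carry that limit and nothing withdraws it, so the meaning should be stated.

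***d* is not the primary analysis.** A reader might infer that *d* alone carries the study's conclusion. It does not. The primary efficacy analysis is an ANOVA on CAPS-4 change, *d* is an additional item among the secondary analyses, and the overall objective also covers safety. Still, *d* is the only effect-size method offered for a stated aim.

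**The bias is small.** Steps 3 and 4 confirm this. The documents do not support a claim that uncorrected *d* will by itself lead to undersized trials.

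**Nothing is concealed.** SAP 6.0 says openly that the sample is small and that pilots are often underpowered. Group n, mean and SD are planned, so a reader could rebuild an interval for a between-arm *d*. That is correct, and the gap is an omission, not a plan to withhold. But the reader would first have to choose the contrast and the SD, and those choices belong in the plan.

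**The figures depend on the form assumed.** If *d* were within-arm, the intervals in step 2 would not apply. That is so, and it shows why *d* needs a definition.

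**Conclusion.** The concern holds as a gap in estimation and reporting. The plan gives a named aim, effect-size estimation, no measure of precision and no definition of the quantity. Under the assumed between-arm *d* of 1.0, the 95% CI is about 2.1 units wide at 12 v 6 and 2.4 at 6 v 6, and includes zero in both cases. That is the substance of the point. The 5% or 8% bias (3.8% with the three-arm error term) is worth removing because removal is nearly free, not because it would change a decision.

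The power phrase needs clarifying; it is not an established error. The Protocol's effect sizes for all outcomes and the SAP's *d* for CAPS-4 alone do not match.

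The numbers rest on assumed values of *d*, a between-arm contrast and a two-group pooled SD, none of which the documents fix. The wide intervals hold across the whole assumed range of 0.5 to 1.5.

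**What to change.** 1. In SAP 8.9.2.1, for CAPS-4 change from baseline to visit 13, define the effect size by pairwise dose contrast and name the SD. The change-score SD would match the primary analysis; whichever is chosen should be stated.
2. In place of Cohen's *d* alone, report Hedges' *g* and the raw CAPS-4 mean difference for each contrast, each with a 95% CI.
3. In Protocol 12.0, delete the reference to statistical power, or limit it to planning later studies across the range of the CI.
4. Reconcile Protocol 12.0 with SAP 8.9.2.1 on which outcomes and time points get an effect size.

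The cost is a wording change in both documents, a little more computation and a slightly smaller reported effect. No new subjects, visits or data are needed, and the primary ANOVA and its type I error do not change. The definitions should be fixed before the primary efficacy analysis, which SAP 8.10 places after all subjects complete Stage 2.
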